6.0 STRATIFICATION/DESCRIPTIVE FACTORS/RANDOMIZATION SCHEME

6.1 The patient will undergo a bilateral operation. At the end of the surgery, hemostasis will be performed with PosiSep X placed in the ethmoid cavity on one side and PuraSinus in the other ethmoid cavity. The randomization will occur using the envelope method to determine which ethmoid cavity will receive PuraSinus and which ethmoid cavity will receive PosiSep X.

Prior to the start of this trial, a randomization list will be generated and sealed opaque envelopes will be created for each participant in the study. Each envelope will instruct which ethmoid cavity (RIGHT or LEFT) will receive PuraSinus. During the surgery, after a total ethmoidectomy has been performed bilaterally by the surgeon, the research coordinator or research staff will open the assigned envelope and have the surgeon read which side the PuraSinus should be applied to. The contralateral ethmoid cavity will receive PosiSep X. The research staff or research coordinator will verify that the intervention (PuraSinus) was applied to the assigned ethmoid cavity.

7.0 STUDY AGENT ADMINISTRATION OR INTERVENTION AND TOXICITY MANAGEMENT PLAN

7.1 Treatment Strategy – The treatment phase begins upon introduction of PuraSinus and bioresorbable nasal dressing into the study patient at the time of surgery

a. Patient Preparation – The patient should be prepared for the planned surgical procedure according to standard surgery center procedures

b. Surgical Extent and PuraSinus Placement

- The technique of total ethmoidectomy should be the same on both sides
- Randomization of the ethmoid cavity to treatment assignment using the envelope method will occur after successful completion of total ethmoidectomy.
- PuraSinus must be used according to the Instructions for Use (IFU).
- Bioresorbable hemostatic packing materials (PosiSep X) will be placed in the opposite ethmoid cavity. Bioresorbable packing will be used according to the IFU.

c. Follow-Up Schedule

The follow-up period begins immediately post-treatment (once the patient exits the operating room). The patient will undergo follow-up assessments including endoscopic examination at three (3) post-operative visits at week 1, week 4, and week 12. A postoperative endoscopic debridement of the ethmoid cavities

will be performed bilaterally at week 1. A second debridement during week 4 is performed if clinically necessary as determined by the surgeon. Risks associated with debridement and nasal endoscopy include possible pain, bleeding, discomfort, irritation, headache, and sneezing.

An overview of the assessments to be performed at baseline and each follow-up interval along with required timing is provided in Table 1. Protocol-required visits occurring outside of the specified date range will be considered and reported as protocol deviations.

7.3 Criteria for removal from treatment (such as undue toxicity, progression of disease, etc.)

7.31 A patient may always be removed from treatment whenever he/she wishes.

7.4 Ancillary treatments.

7.41 Any ancillary treatment of the ethmoid cavity with steroid-eluting stents will not be allowed. If steroid-eluting stents are placed in the ethmoid cavity due to clinical indication, that participant will be excluded from the study.

7.42 Ancillary treatment with oral antibiotics, oral steroids, nasal saline irrigations, or topical steroids as part of standard postoperative care is allowed.

8.0 ASSESSMENT OF SAFETY

8.1 Side effects/Toxicities to be monitored.

8.1.1 Risks or side effects associated with PuraSinus:

- Nasal irritation
- Hypersensitivity reaction
- Intranasal bleeding
- Localized infection (bacterial, fungal colonization or viral) in the nose
- Nasal burning
- Nasal dryness

8.1.2 No long-term toxicities will be monitored as PuraSinus will be removed from the ethmoid cavity 1 week after surgery.

8.3 Adverse Event Reporting: Adverse events may occur during the investigational procedure or during the follow-up phase. Adverse events occurring during the baseline assessment and/or other pre-investigational procedures will be documented in the patient's medical record.

8.3.1 Each adverse event will be reported in a timely fashion to the principal investigator. The principal investigator is responsible for ensuring that all adverse events are appropriately captured and when applicable, reported to the government, ethics committee, and the sponsor. Each adverse event will be recorded in the corresponding patient's file. Participating investigators will make a determination as to the relationship of each adverse event to the surgical or endoscopic procedure, comorbidity, or the investigational device. Adverse event reports will identify the date of onset, severity, and duration. All adverse events will be monitored until they are adequately resolved or explained.

8.3.2 Places for submitting reports: The principal investigator will report the above to the University of Southern California IRB.

8.4 Study site monitoring will be performed by an otolaryngology faculty member at the University of Southern California who is independent of the study. The study monitor will be tasked with assessing the study's overall progress, including but not limited to the trial's ability to keep accurate records and to report study related data, including adverse events, to the study sponsor in a timely fashion. In order to appropriately monitor the progress of the study, the study monitor will have access to the source documents and other information necessary to ensure investigator compliance with the protocol and applicable rules and regulations and to assess the progress of the clinical investigation.

The study monitor will maintain contact with investigators and study coordinators by phone, email, or on-site visits. Monitoring will be performed concurrently during the period of patient enrollment to completion of the final patient follow-up visit. The frequency of monitoring may occur as often as a biweekly basis. Monitoring will ensure continued protocol compliance and accurate reporting of data, adverse events, protocol deviations and product accountability.

9.0

CLINICAL AND LABORATORY EVALUATIONS AND STUDY CALENDAR

All visits will occur during typical standard of care appointments for patients undergoing endoscopic sinus surgery.

Parameter	Pre-Surgery	Surgery	Week 1	Week 4	Week 12
Sociodemographic Questionnaire, informed consent	X				
Randomization: placement of PuraSinus		X			
Nasal endoscopy video recording			X	X	X
Patient-reported pain during debridement			X		
Endoscopic debridement procedure			X	X ¹	
Time required to perform debridement			X	X ²	
Bleeding			X	X ²	
Review of video-endoscopies by independent blinded surgeon for: 1. Lund-Kennedy score (mucosal edema, crusting, secretions, adhesions, polyps) 2. Residual packing amount 3. Adhesions			X	X	X
Review of video-endoscopy by independent blinded surgeon for: Need for further intervention				X	
Ascertainment of side effects and adverse events		X	X	X	X

Table 1. Study Calendar

¹if clinically indicated.

²if debridement performed

10.0

CRITERIA FOR EVALUATION AND ENDPOINT DEFINITIONS

The outcome status of all eligible patients will be reported. All eligible patients who begin treatment and attend the week 1 postoperative visit will be included in the analysis.

ENDPOINT DEFINITIONS

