3.0 STUDY DESIGN

3.1 Type of Study

This is a prospective randomized controlled multicenter study at the University of Southern California that will enroll at least 30 participants who satisfy criteria to compare the efficacy of PuraSinus versus standard of care in patients undergoing endoscopic sinus surgery. The study will utilize an intra-patient control design to assess the safety and efficacy of PuraSinus compared to PosiSep X on the contralateral side. The study patients will undergo PuraSinus placement in one nasal cavity following traditional endoscopic sinus surgery. The study is blinded, meaning that patients will be blinded throughout the study duration to which side received PuraSinus placement. The independent surgeon performing review of the video-endoscopies will also be blinded to which side received PuraSinus.

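### Section 8.3.1 does not require the side of an adverse event or its relationship to PosiSep X, so the section 3.1 safety comparison is not secured for local events captured only as adverse events

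*Combined protocol and SAP*

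**What the plan says.** Section 3.1 gives the purpose of the intra-patient design as "to assess the safety and efficacy of PuraSinus compared to PosiSep X on the contralateral side". Section 6.1 randomises the side: "Each envelope will instruct which ethmoid cavity (RIGHT or LEFT) will receive PuraSinus". The other cavity receives PosiSep X, and staff verify that PuraSinus went to the assigned side.

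Section 8.3.1 sets the adverse event rules:

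- Content of the report: "Adverse event reports will identify the date of onset, severity, and duration".
- Causality: investigators judge the "relationship of each adverse event to the surgical or endoscopic procedure, comorbidity, or the investigational device".
- Place of recording: the file of the individual patient.

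Section 8.1.1, under "Risks or side effects associated with PuraSinus", lists six items. There is no matching list for PosiSep X. Table 1 in section 9.0 has a single row, "Ascertainment of side effects and adverse events", at surgery and weeks 1, 4 and 12, with no split by side. Section 13.2 describes no adverse event analysis.

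**The concern.** In a parallel-group trial the patient identifies the treatment. Here the patient does not, because each patient has both products. A local event entered for a patient without its side belongs to the PuraSinus cavity, the PosiSep X cavity or both, and the record does not say which.

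The causality list does not fill the gap. It offers the study device but not the comparator packing, so an event thought to come from PosiSep X has no category of its own. The protocol itself recognises a risk specific to that product: exclusion criterion 5.2(f) rules out shellfish allergy because of the chitosan content.

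At stake is the safety half of the purpose stated in section 3.1. Side is easy to ask for when an event is reported and may be impossible to recover later.

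**Working it through.** No figure in the plan attaches to this point. The only calculated figure, the 83% power in section 13.1, concerns pain and does not change. The check is therefore mainly a reading of the sections against each other, with short arithmetic on what an adverse event table could show.

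**1. Is side asked for elsewhere?** Yes. Pain is rated for each cavity (10.1), debridement time is recorded for each cavity (10.2), and video files are labelled by laterality (12.1). Section 8.3.1 has no such requirement.

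**2. Which listed side effects already have side-level data?** Take the six items in 8.1.1 against sections 10.3, 10.4 and 12.1:

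| Item in 8.1.1 | Side-level measure outside adverse event reports |
|---|---|
| Intranasal bleeding | Graded 0-3 by a blinded assessor from video, at the week 1 debridement and at week 4 if debrided; nothing between visits |
| Localised infection | Partial: the top level of the Lund-Kennedy discharge item, weeks 1, 4 and 12 |
| Irritation | None |
| Burning | None |
| Dryness | None |
| Hypersensitivity | None; where systemic, a side field would not help |

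Adhesions, edema, crusting and polyps are also graded from video, although they are not in the 8.1.1 list. So one of six items has a direct measure limited to debridement, one has a proxy, three local symptoms have nothing, and one may not be assignable in this design at all.

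**3. What does a patient-level count show?** Suppose k of 30 patients have a local event and side is not recorded. All 30 were exposed to both products, so the rate is k/30 for each and the difference is k/30 - k/30 = 0 by construction. If each event was in fact in one cavity only, the true paired difference could lie anywhere from -k/30 to +k/30. As an illustration, with an assumed k = 6 the range is -6/30 to +6/30, that is -20 to +20 percentage points, and the record is the same throughout.

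**4. What would recording side add?** Side was randomised, so a tabulation by side gives a comparison by allocation that needs no causality judgement. Its precision is low:

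- With no events in 30 cavities, the one-sided 95% upper bound is 1 - 0.05^(1/30) = 0.095, or about 9.5%.
- In a two-sided exact sign test on discordant pairs all in one direction, five pairs give 2 × 0.5^5 = 0.0625 and six give 2 × 0.5^6 = 0.031. At least six are needed to fall below 0.05.

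The table would therefore be descriptive.

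**The case against.** Five objections carry weight.

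- **Side-level safety data exist.** A reader might infer from 8.3.1 that the contralateral comparison cannot be made at all. The documents do not support that. The video outcomes in 10.3 and 10.4 cover several local complications, and verified allocation links side to product. This stands, and it confines the point to events seen only as adverse events.
- **The sentence on report content may be a minimum.** It does not mention even a description of the event, so it is hard to read as a closed list. The adverse event form is not in the documents and may hold a side field. This also stands: what can be said is that the protocol does not require side, not that the reports will lack it.
- **Safety is not a listed objective or outcome.** Sections 2.1, 2.2 and 3.3 do not name it, and no planned analysis fails for want of the field. True, and it limits the importance of the point. Section 3.1 still states safety as a purpose of the design.
- **The causality list need not bias attribution.** A reader might infer that it pushes product-related events towards PuraSinus. Nothing shows this. An investigator could place a PosiSep X event under the surgical procedure, since packing is placed at the end of surgery. The defect is a missing category.
- **Not every event without a side is uninformative.** One judged related to the study device points to PuraSinus. It does so through the judgement of an investigator who may know the allocation, which is weaker than a tabulation by randomised side, but it is information.

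**Conclusion.** The point holds in a limited form. Section 3.1 states a within-patient safety comparison, while section 8.3.1 requires neither side nor relationship to the comparator and section 13.2 plans no summary. The comparison is therefore not secured for irritation, burning, dryness, infection beyond the discharge score, and bleeding between visits. It is available, descriptively, for bleeding at debridement, adhesions and the Lund-Kennedy items.

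No event rate can be attached, because the documents give none. The primary endpoint, the sample size and the planned tests are untouched. The change should still be made, because the causality list does not fit a design in which every patient receives both products and lost side information may not be recoverable.

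This rests on two assumptions: that the unseen form follows 8.3.1 without adding side, and that the bleeding grade in 10.3, which does not itself mention each cavity, is given by side as the video labelling in 12.1 implies.

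**What to change.** In section 8.3.1, add side (left, right, both, not attributable) to the required adverse event fields, and add relationship to PosiSep X to the causality determination alongside the study device.

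In section 13.2, add a descriptive within-patient summary of local adverse events by product. For each event type, give the number of patients with the event on the PuraSinus side only, the PosiSep X side only, both sides, or not attributable. No test is needed.

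The cost is two form fields, brief protocol text and one small table, with no extra visits. Recording left or right does not tell the patient which product is on which side. Systemic events, and symptoms that do not lateralise, will remain unassigned.

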10.1 Patient-reported pain during debridement

During postoperative debridements in week 1, the surgeon will topically anesthetize both nasal cavities. The surgeon will then begin debridement of the left ethmoid cavity, removing any residual packing, blood, secretions, obstructive crusting from that ethmoid cavity. The surgeon will then perform the same debridement in the right ethmoid cavity. Afterwards, the patient will be asked to rate their pain on a scale from 1-10 with 1 being the least pain and 10 being the most extreme pain during the procedure for each ethmoid cavity (left and right), which will be recorded by the research staff.

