3.3 Study outcome measures

3.3.1 Primary outcome

- Patient reported pain (1-10) during postoperative debridement of ethmoid cavity 1 week after surgery

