13.0 STATISTICAL CONSIDERATIONS

13.1 Sample size

There are no published data available regarding trial outcomes for the PuraSinus hydrogel product. A study from Canada, reported pain during removal of a comparable bioresorbable packing (Nasopore) as 4.03/10 (SD 2.80) among 30 subjects.⁵ In our clinical practice, PosiSep X bioresorbable packing removal is usually rated approximately 5-6/10 (it is uncomfortable) and PuraSinus removal around a 2/10. Using a mean difference of 2 (4.03 with bioresorbable packing versus 2 with hydrogel), a more conservative SD of 3.5 and testing at a 2-sided alpha=0.05, a sample of 30 subjects will provide 83% power to detect this difference in paired measures using a Wilcoxon signed rank test.

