13.2 Statistical analysis

The sample will be described by demographic and clinical characteristics, summarizing continuous variables by mean (SD) and categorical variable by frequency (percent). All trial outcome comparisons will be tested at a two-sided p-value of 0.05.

Primary objective: To investigate the efficacy of PuraSinus in reducing patient pain during postoperative debridement after endoscopic sinus surgery compared to PosiSep X.

The primary outcome of pain at 1-week debridement, evaluated on a 1-10 scale, will be compared between interventions using a Wilcoxon signed rank test (paired test). The median and interquartile range of the pain score will be summarized for each intervention. To consider side (right/left), a generalized linear mixed effects model will analyze the pain score as a dependent variable, with a random intercept for participant; independent variables will include randomized intervention, side, and an interaction of intervention-by-side (testing if the intervention effect may differ by side).

Secondary objectives:

- To assess the time needed to perform postoperative debridements in patients with PuraSinus in their ethmoid cavity after endoscopic sinus surgery
- To assess the efficacy of PuraSinus in preventing postoperative complications from endoscopic sinus surgery (adhesions, bleeding, crusting, edema)
- To assess the amount of PuraSinus retained in the ethmoid cavity postoperatively
- To assess the need for further intervention postoperatively in patients

Continuously measured secondary trial outcomes (time required for debridement; Lund-Kennedy Endoscopy score) will be compared between interventions using Wilcoxon signed rank and generalize mixed effects model as described above. Amount of bioresorbable dressing retained will be presented as proportions, with 95% confidence intervals (in the categories of none, <50%, ≥50%). Bleeding during debridement and adhesions will be presented as proportions. The need for further intervention will also be presented as proportion (with 95% confidence interval) of participants required further surgical or oral steroid intervention.

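### The primary pain score has no explicit no-pain answer, so painless and slightly painful debridements may share the score 1

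*Combined protocol and SAP*

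**What the plan says.** The primary outcome in 3.3.1 is "Patient reported pain (1-10) during postoperative debridement of ethmoid cavity 1 week after surgery". The synopsis gives the same range, and 13.2 repeats it: "The primary outcome of pain at 1-week debridement, evaluated on a 1-10 scale". Section 10.1 supplies the anchors. Both nasal cavities are topically anesthetized, the left and then the right ethmoid cavity is debrided, and the patient is then asked to "rate their pain on a scale from 1-10 with 1 being the least pain and 10 being the most extreme pain", separately for each side. Zero is not offered, and no point is labelled as absence of pain.

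Section 13.1 draws its planning values from two sources. A published study "reported pain during removal of a comparable bioresorbable packing (Nasopore) as 4.03/10 (SD 2.80) among 30 subjects". From the investigators' own practice, "PosiSep X bioresorbable packing removal is usually rated approximately 5-6/10 (it is uncomfortable) and PuraSinus removal around a 2/10". The calculation then proceeds "Using a mean difference of 2 (4.03 with bioresorbable packing versus 2 with hydrogel"). Both sources are expressed out of 10; neither is said to start at 0 or at 1.

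**The concern.** The rationale in 1.0 is that a thin layer of hydrogel should leave little to debride and cause little discomfort. The trial therefore expects its test product to score low, where this instrument is least clearly defined. A patient who felt nothing must still record 1, and a patient who felt a little may record 1 as well.

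If that happens, more PuraSinus ratings than PosiSep X ratings are raised to the floor, because more of them would have been 0. The measured reduction then understates the true one. Pairs that would have differed by 0 against 1 become ties and drop out of the signed rank statistic. A low PuraSinus median, which 13.2 plans to report, could not be read as painless or as slightly painful.

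The protocol's other graded outcomes do have an explicit absent level: bleeding in 10.3, the Lund-Kennedy items and adhesions in 10.4, and residual dressing in 10.5. The sole primary endpoint does not.

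**Working it through.** **The plan's own figure.** Inputs from 13.1: difference 2, SD 3.5, 30 pairs, two-sided alpha 0.05, Wilcoxon signed rank test. Read 3.5 as the SD of the paired difference and apply the test's asymptotic efficiency of 3/π. The effective n is 30 × 0.955 = 28.65, the noncentrality is (2/3.5) × √28.65 = 3.06, and noncentral t power is 83.9%. Simulating the signed rank test on normal differences gives 84.0%. The stated 83% reproduces.

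**What must be assumed.** The documents give no PuraSinus SD, score distribution, within-patient correlation or planning scale. I take integer beta-binomial scores on 0-10, with PosiSep X at mean 4.03 and SD 2.80, and PuraSinus at mean 2 and SD 1.5, 2.0 or 2.8. Correlations are 0, 0.3 and 0.5.

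**Shift in the mean if every 0 is recorded as 1.** Each side's mean rises by its share of zeros, so

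difference on 1-10 = (4.03 + z_Posi) − (2 + z_Pura) = 2.03 − (z_Pura − z_Posi).

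For a beta-binomial with mean proportion m, ρ = [SD²/(10m(1−m)) − 1]/9, a + b = 1/ρ − 1 and a = m(a + b).

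- PosiSep X: 7.84/(10 × 0.403 × 0.597) = 3.26, ρ = 0.251, a + b = 2.985, which gives z_Posi = 0.108.
- PuraSinus, SD 2.0: 4/1.6 = 2.5, ρ = 1/6, a = 1, b = 4, which gives z_Pura = 4/14 = 0.286.
- The same steps give 0.160 at SD 1.5 and 0.495 at SD 2.8.

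**Signed rank power, 30 pairs, correlation 0.3** (1,500 simulated trials per setting, Monte Carlo standard error about 1 point or less). In the 'spread' column the same pain is scaled over 1-10 as 1 + 0.9 × score, rounded, instead of 0 being merged into 1.

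| PuraSinus SD | Share at 0 | Shift | Difference after merging | Power, 0-10 | Power, merged | Power, spread |
|---|---|---|---|---|---|---|
| 1.5 | 0.160 | 0.05 | 1.98 | 0.97 | 0.98 | 0.96 |
| 2.0 | 0.286 | 0.18 | 1.85 | 0.95 | 0.94 | 0.95 |
| 2.8 | 0.495 | 0.39 | 1.64 | 0.88 | 0.79 | 0.91 |

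Across the three correlations, merging changes power by about +3 to −1 points at SD 1.5 to 2.0, and the largest loss, at SD 2.8, is about 9 points. Tied pairs rise from about 10-16% to 16-25%. Spreading changes power by about −2 to +3 points. It also lowers the mean difference (to 1.74-1.87), but mainly because the unit has changed: 2.03 × 0.9 = 1.83.

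**Other shapes.** With rounded and clipped normal scores (latent means 4.03 and 2, SD 2.0 to 3.5), merging costs about 0.2 point and 0 to 3 points of power. At SD 2.8 and correlation 0.3 the difference goes from 1.73 to 1.54, but its SD also falls, from 2.93 to 2.70. The standardized effect therefore moves only from 1.73/2.93 = 0.59 to 1.54/2.70 = 0.57, and power from 87% to 85%. With a PosiSep X mean of 5.5, the midpoint of the range from practice, the difference falls by about 0.2 to 0.3 point and power stays at 94% or more.

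**The case against.** The lowest answer is the bottom of the scale and can be read as including no pain. A patient who reads it so gives 1 for nothing and 2 for slight pain, and nothing is merged. This stands: a reader might infer that painless and slightly painful debridements necessarily score alike, but 10.1 does not establish that. What remains is that the anchor allows two readings. The within-patient comparison limits the harm without making a score of 1 interpretable.

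The planning value of 2/10 may itself have come from a 1-10 scale. The planned difference would then already contain the floor, and nothing would be lost against plan. If the two means came from differently anchored scales, the difference of 2 mixes them. Section 13.1 does not settle this, so the shrinkage is conditional.

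A reader might also infer that a mean of 2 on 1-10 puts most PuraSinus ratings at the floor, and take that as proof of harm. That uses a different premise from the shrinkage figures, and relabelling the same ratings 0-9 would leave the share at the lowest category unchanged.

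Finally, the 9-point loss needs PuraSinus to have the control's spread at half its mean, with about half of its sides at exactly 0. The case cannot be ruled out: with SD 2.8 on both sides, 2.8 × √(2(1 − r)) equals the plan's 3.5 at r = 0.22. But the plan itself calls 3.5 conservative, and the other scenarios lose little or nothing. The share of painless debridements is not a stated endpoint, so failing to report it breaks no commitment.

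**Conclusion.** The point holds as a minor one. The primary endpoint lacks a no-pain answer in the region where the test product is expected to score, so low scores are ambiguous. If painless and slightly painful debridements share the score 1, the reduction is biased toward zero by about 0.05 to 0.4 point of about 2, under beta-binomial scores on 0-10 with every 0 recorded as 1. Power then changes little in most scenarios and falls by up to about 9 points only when about half of PuraSinus sides are painless. If patients spread their answers over 1-10, there is little or no power loss.

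A reader might go further and conclude that the analysis is invalid or the sample size miscalculated. Neither follows. The signed rank test keeps its validity, merging works against finding a benefit rather than creating one, and the 83% reproduces from its stated inputs.

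**What to change.** Before any ratings are collected, replace the range in the synopsis, 3.3.1, 10.1, 13.2 and on the data collection form with a 0-10 numeric rating scale, 0 = no pain and 10 = most extreme pain. At minimum, label the lowest point explicitly as no pain; doing so on a 1-10 scale would also remove the ambiguity. Keep the Wilcoxon signed rank test as planned. Add a descriptive paired summary of painless cavities: the numbers of patients painless on both sides, on PuraSinus only, on PosiSep X only, and on neither. State in 13.1 which scale the 4.03 and the 2 come from.

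If ratings have already been collected, keep one scale for every participant and report the floor as a limitation.

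The cost is a wording change in four places and on one form, plus one sentence in 13.1. No extra patients, visits or staff are needed.
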